7.3 Sample Size

Assuming a response rate for Barrett's esophagus with EndoRotor® ablative therapy of 80%, and for cryoablation of 50%, the study will have over 95% power to demonstrate non-inferiority (NI), given a NI delta of 10%, of EndoRotor® to cryoablation and will have 91.6% power to demonstrate superiority of EndoRotor® over continued ablative therapy using a sample size of 110 evaluable subjects, 55 in each treatment group.

7.4 Statistical Analysis

The Primary effectiveness endpoint will be compared across treatment arms using a logistic regression, where the predictor variable is treatment arm with EndoRotor® coded 1 vs 0 for cryotherapy or ablative therapy (i.e., control). Covariates included in the model will be: subject's age, dysplasia (low-grade or high-grade), length of Barrett's lesion in cm, and duration of disease (months). The lower boundary of the predicted proportion

difference will be used to compare the two arms for the non-inferiority test and for the subsequent superiority test. In the event that missing data are present in the ITT analysis population, then multiple imputation will be performed with SAS procedures MIIMPUTE and MIANALYZE, as described in section 7.5.

The secondary endpoint, percentage reduction, will be compared using a Wilcoxon rank-sum test. In the event of missing data, The ITT analysis will be performed with data imputed by multiple imputation.

In the event of missing data, sensitivity analyses will be performed for the ITT analysis population using best case and worst case analyses as described below. Discrepant findings will be followed by tipping point analyses.

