4.5 Clinical Sites & Enrollment

A minimum of three (3) and up to five (5) research sites in the United States will participate in this pivotal study. The sites will enroll a total of 120 subjects meeting all inclusion and exclusion criteria to reach a total of 110 evaluable subjects, allowing for 10 subjects lost to follow-up. It is anticipated that there will be a total of 55 evaluable subjects in each arm. Once the informed consent process is completed and final study eligibility has been confirmed, the patient will have the EndoRotor or continued ablative therapy procedure.

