5.2 Randomization Scheme

Randomization will be performed within 2 weeks of the procedure separately within each site using a 1:1 ratio

to EndoRotor® or continued ablative therapy, with blocking to be specified in separate randomization documentation. A total of 110 sealed envelopes, 55 of which contain a designation of "EndoRotor® resection" and the other 55 with the designation "Continued Ablative Therapy" will be produced. The investigator will have access to the envelopes and will designate one other person at each site to be in charge of distributing the envelopes during recruitment. The envelopes will be stored in a locked cabinet within a secure locked office at the site. If patients are lost to follow-up, additional envelopes will be provided to the site.

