7.5 Missing Data

1. If there are missing primary endpoint data, then ten imputations of missing binary primary endpoint will be produced using SAS PROC MI using the Markov chain Monte Carlo algorithm. The seed used to begin random number generation will be 20170623. The following variables will be used as predictors: site, subject's age, dysplasia (low-grade or high-grade), length of Barrett's lesion in cm, and duration of disease (months). Analysis with SAS PROC MIANALYZE will follow.
2. For the secondary endpoint, percentage reduction, ten imputations will be produced for the randomized cohort using SAS PROC MI. The seed used to begin random number generation will be 20170623. The Markov chain Monte Carlo method will be used to compute full imputations using the following variables: site, subject's age, dysplasia (low-grade or high-grade), length of Barrett's lesion in cm, and duration of disease (months). Analysis with SAS PROC MIANALYZE will follow.

The following secondary analyses will be performed to assess the sensitivity of the results to missing data for the primary effectiveness endpoint.

- The best-case scenario will assume success for all missing data treated with EndoRotor and failure for all missing data treated with control.
- The worst-case scenario will assume failure for all missing data treated with EndoRotor and success for all missing data treated with control.
- If the best and worst case analyses lead to different statistical conclusions, then a tipping point analysis will report the proportion of successes or failures for each arm at point the statistical conclusion would change.

A similar approach will be used for the continuous percentage secondary endpoint. Best case will assume 100% removal for EndoRotor® and 0% for control; worst case will assume 0% removal for EndoRotor® and 100% for control; If the results differ using the two imputation rules, then the imputed values will be incremented on 1% values until the point where the conclusion changes is identified.

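### Randomization is stratified by site but the primary logistic model omits site, so the interval for the risk difference will be somewhat too wide if site predicts outcome

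*Combined protocol and SAP*

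**What the plan says.** Section 5.2 allocates subjects "separately within each site using a 1:1 ratio", with blocking. Section 4.5 plans three to five sites.

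Section 7.4 compares the arms by logistic regression on treatment plus four covariates, introduced by "Covariates included in the model will be" and listed as "subject's age, dysplasia (low-grade or high-grade), length of Barrett's lesion in cm, and duration of disease (months"). Site is not among them. The lower bound of the predicted proportion "difference will be used to compare the two arms for the non-inferiority test and for the subsequent superiority test", so both primary tests are on the risk-difference scale. Section 7.8 confirms that superiority uses the same model.

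Site appears in two other places. Section 7.5 begins its list of imputation variables with it ("The following variables will be used as predictors: site"). Section 7.8.1 summarizes success by site and applies Fisher's exact test at alpha 0.15, but states no consequence for the primary model. The documents give no reason for leaving site out of 7.4.

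**The concern.** Balancing the arms within site removes between-site variation from the comparison of arms. A model without site still counts that variation as noise, so the reported standard error exceeds the estimator's real variability whenever success rates differ between sites.

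The plan makes such differences plausible. The investigator chooses RFA or cryotherapy in the control arm (5.5.3), ablation follows each institution's standard of care (1.1), and the resident pathologist reads the histology (5.8.3) with no central reading described. At stake are some power and an unnecessarily wide interval. Section 7.8.1 also leaves open whether site would be added after its test is seen, which would be a data-driven change to the primary model.

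**Working it through.** **Inputs.** From the plan: 55 per arm, 80% versus 50%, margin 10 points, two-sided 0.05, three to five sites, risk-difference scale. Assumed, because the documents are silent: how success rates vary by site. Sites are taken as equal in size.

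**The plan's own power.** The unpooled SE is √[(0.8×0.2 + 0.5×0.5)/55] = 0.0863. The pooled SE under the null is √[2×0.65×0.35/55] = 0.0910. Superiority power is Φ[(0.30 − 1.96×0.0910)/0.0863] = 92.1%, against 91.6% stated in 7.3. Non-inferiority power is Φ[(0.30 + 0.10)/0.0863 − 1.96] = 99.6%, against over 95% stated. Both figures reproduce. Neither uses covariates, so the omission of site does not affect them.

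**SE excess with no treatment difference and no other covariates.** In large samples the ratio of reported to true SE is √[p̄(1−p̄) / mean of pₛ(1−pₛ)], where pₛ is the success rate at site s.

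- 40/50/60%: √(0.25/0.2433) = 1.014
- 30/50/70%: √(0.25/0.2233) = 1.058
- 25/40/50/60/75%: √(0.25/0.221) = 1.064

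At 55 per arm the unpooled SE is itself low by a factor of about √(54/55) = 0.991, which gives net ratios of 1.005, 1.048 and 1.054. Simulation agrees: about 1.00, 1.05 and 1.05-1.06. Two-sided type I error at 30/50/70% is about 3.6%. The right baseline for that figure is 4.7%, not 5%, because discreteness alone gives 4.7% when there is no site effect.

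**Power at 80% versus 50%.** Simulation used 20,000 trials per setting, the model of 7.4 with four non-prognostic covariates, and the standardized risk difference with a delta-method SE. Site effects are given as an SD on the logit scale.

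| Site SD | Control rates (5 sites) | SE ratio (formula) | Power without → with site, 3 sites | 5 sites |
|---|---|---|---|---|
| 0 | all 50% | 1.00 | 92.2 → 92.4% | 92.5 → 92.9% |
| 0.25 | 41-59% | 1.007 | 92.8 → 93.0% | 92.5 → 93.2% |
| 0.5 | 33-67% | 1.026 | 93.3 → 94.0% | 92.9 → 94.0% |
| 1.0 | 20-80% | 1.10 | 94.5 → 96.0% | 93.8 → 96.0% |

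Non-inferiority power exceeds 99% throughout. The estimate itself varies equally with and without site (0.0805 both ways at SD 1.0, three sites), so the loss lies in the reported SE. With three sites, the reported SE without site is about right at SD 0.5 (0.0852 against 0.0859) and clearly too large only at SD 1.0 (0.0853 against 0.0805).

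**Smaller true difference (assumed 75% versus 50%).** The SE ignoring site is √[(0.1875 + 0.25)/55] = 0.0892. If the SE ratio is again 1.05, the true SE is 0.0850. Power is then Φ[(0.25 − 1.96×0.0892)/0.0850] = 81% without site and Φ[0.25/0.0850 − 1.96] = 84% with it. At a ratio of 1.10 the true SE is 0.0811, and power is 82% against 87%.

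**The case against.** The strongest reply is that nothing in the documents shows site to be prognostic. Sections 4.8, 9.3 and 9.4 describe major referral centers, experienced investigators and common training, and the four planned covariates may absorb some referral differences. Excesses of 5-6% need site rates 40 to 50 points apart. The error is conservative, stated power is met without site, and 7.8.1 does examine site. All of this stands. It limits the size of the point but gives no reason to leave out a factor the trial already randomizes by.

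Adding site also has a cost. About 0.2×55 + 0.5×55 = 38 failures are expected. The model has six parameters, and five sites would make ten, or about four failures per parameter. In the simulation the delta-method SE with site was slightly too small (0.0822 against 0.0860 at SD 0.5, three sites), and one-sided type I error was about 0.028-0.033. Part of the power gain in the table therefore reflects that optimism; a small gain appears even with no site effect.

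Three stronger readings are tempting, and the documents do not support them:

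- **That the SE is certainly too large.** This depends on between-site variation, which the documents do not give. It also applies only to the risk difference. On the log-odds scale the SE is smaller without site (0.463 against 0.488 at SD 0.5, three sites), because the coefficient shrinks too.
- **That site in the imputation model but not in the analysis model is a defect.** An imputation model may properly carry more variables than the analysis model.
- **That omitting site risks a false claim.** The direction is conservative.

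**Conclusion.** The point holds as a modest, conditional loss of efficiency. The primary model omits the factor by which randomization is stratified, and nothing elsewhere in the plan repairs that. If site is prognostic, the interval for the risk difference is somewhat too wide: a net 0% at 40/50/60%, and about 5-6% at 30/50/70% or five sites from 25% to 75%. A 5% excess gives 110 subjects the interval width of about 110/1.05² = 100.

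The power cost at the planned rates is about 0 to 2 points, and the stated 91.6% and 95% are still met. At a 25-point true difference with large site variation it may reach several points (about 3 to 5 in the arithmetic above). These sizes rest on assumed site rates and equal site sizes. With no site effect there is no loss.

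**What to change.** Before unmasking, amend 7.4 so that the primary logistic model includes site as a fixed effect for both the non-inferiority and superiority tests, with the standardized risk difference kept as the test scale. State a pooling rule in advance: for example, merge any site with fewer than about 10 subjects, or with no successes or no failures, into a combined stratum. Specify how the SE of the risk difference is computed, preferably with a small-sample correction, given the slight optimism seen above. State in 7.8.1 that its result does not change the primary model. If the sponsor prefers to leave site out, give the reason.

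The cost is a few SAP sentences, 2 to 4 degrees of freedom and some sparse-data risk. Neither the sample size nor trial conduct changes.

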7.5 Missing Data

1. If there are missing primary endpoint data, then ten imputations of missing binary primary endpoint will be produced using SAS PROC MI using the Markov chain Monte Carlo algorithm. The seed used to begin random number generation will be 20170623. The following variables will be used as predictors: site, subject's age, dysplasia (low-grade or high-grade), length of Barrett's lesion in cm, and duration of disease (months). Analysis with SAS PROC MIANALYZE will follow.
2. For the secondary endpoint, percentage reduction, ten imputations will be produced for the randomized cohort using SAS PROC MI. The seed used to begin random number generation will be 20170623. The Markov chain Monte Carlo method will be used to compute full imputations using the following variables: site, subject's age, dysplasia (low-grade or high-grade), length of Barrett's lesion in cm, and duration of disease (months). Analysis with SAS PROC MIANALYZE will follow.

The following secondary analyses will be performed to assess the sensitivity of the results to missing data for the primary effectiveness endpoint.

- The best-case scenario will assume success for all missing data treated with EndoRotor and failure for all missing data treated with control.
- The worst-case scenario will assume failure for all missing data treated with EndoRotor and success for all missing data treated with control.
- If the best and worst case analyses lead to different statistical conclusions, then a tipping point analysis will report the proportion of successes or failures for each arm at point the statistical conclusion would change.

A similar approach will be used for the continuous percentage secondary endpoint. Best case will assume 100% removal for EndoRotor® and 0% for control; worst case will assume 0% removal for EndoRotor® and 100% for control; If the results differ using the two imputation rules, then the imputed values will be incremented on 1% values until the point where the conclusion changes is identified.

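### Section 7.5 imputes a yes/no endpoint and a percentage capped at 100 with PROC MI's normal-theory MCMC method, so the primary ITT logistic regression cannot be run as written

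*Combined protocol and SAP*

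**What the plan says.** Section 7.2 makes ITT (everyone randomized) the primary effectiveness population and has missing primary and secondary endpoint data imputed.

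For the primary endpoint, section 7.5 item 1 says "ten imputations of missing binary primary endpoint will be produced using SAS PROC MI using the Markov chain Monte Carlo algorithm", and then "The following variables will be used as predictors: site, subject's age, dysplasia (low-grade or high-grade), length of Barrett's lesion in cm", with disease duration as the last predictor. For percentage reduction, item 2 says "The Markov chain Monte Carlo method will be used to compute full imputations using the following variables: site, subject's age, dysplasia", and the list continues as in item 1. Both items end with "Analysis with SAS PROC MIANALYZE will follow".

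The analyses that receive the imputed data are in section 7.4. For the primary endpoint: "The Primary effectiveness endpoint will be compared across treatment arms using a logistic regression, where the predictor variable is treatment arm". For the secondary: "The secondary endpoint, percentage reduction, will be compared using a Wilcoxon rank-sum test".

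Neither section gives a rounding rule, minimum or maximum limits, a categorical imputation method, a coding for site, or the statistic to be pooled. Section 7.5 also plans best-case, worst-case and tipping-point analyses. For the percentage, these treat 0 and 100 as the extremes: "Best case will assume 100% removal for EndoRotor® and 0% for control".

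**The concern.** PROC MI's MCMC method draws missing values from a multivariate normal distribution and accepts only numeric variables. Three things follow from the text as it stands.

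- **Primary endpoint.** A missing success/failure outcome is replaced by a real number that is never exactly 0 or 1 and often lies outside that interval. A binary logistic regression needs 0/1. Someone would have to add a step that the plan does not contain.
- **Percentage reduction.** Subjects with complete clearance sit at 100. Normal draws go past 100, and a rank test then orders those imputed subjects above subjects with real complete clearance.
- **Site.** The three to five centres have no natural order. Entered as a code number, site contributes a straight line through arbitrary labels. The text allows indicator variables but does not ask for them.

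At stake is whether the primary ITT analysis can be carried out exactly as pre-specified whenever an outcome is missing, which the plan expects: section 4.5 allows for 10 of 120 subjects lost.

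**Working it through.** **Inputs.** Response rates of 80% and 50%, and 55 evaluable per arm (section 7.3). 120 enrolled and 10 lost (section 4.5), taken here as 5 of 60 per arm. Two-sided alpha 0.05 (section 7.1). Margin 10% (section 7.6).

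**1. The plan's nearest figure.** Section 7.5 gives no figure that can be recomputed. The superiority power in section 7.3 can be. With pooled variance, power = Φ[(0.30 − 1.96·√(2·0.65·0.35/55)) / √((0.16+0.25)/55)] = Φ[(0.30 − 0.1783)/0.0863] = 92.1%, against the stated 91.6%. It reproduces closely and does not depend on the imputation method.

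**2. Normal draws for a binary endpoint.** Take mean p and SD √(p(1−p)).

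| p | SD | above 1 | below 0 | outside 0–1 | share ≥ 0.5 (value after rounding) |
|---|---|---|---|---|---|
| 0.50 | 0.500 | 15.9% | 15.9% | 31.7% | 0.500 |
| 0.65 | 0.477 | 23.2% | 8.6% | 31.8% | 0.623 |
| 0.80 | 0.400 | 30.9% | 2.3% | 33.1% | 0.773 |

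The remaining draws are fractions; none equals 0 or 1. A simulation of 1,000 trials with ten imputations each (120 randomized, 5 missing per arm completely at random) agreed. About 34% of imputed values lay outside 0–1, and 98.5% of completed datasets held at least one such value. A binary logit fitted in Python to one such dataset stopped with an error that the outcome must lie in the unit interval.

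**3. Cost of rounding at 0.5.** Only imputed values move. Device arm: (0.800 − 0.773) × 5/60 = 0.0022, or 0.2 percentage points. Control at 0.50: zero. At 25% missing, the device-arm shift is 0.0266 × 0.25 = 0.7 points. In the simulation, with arm added to the imputation model, the mean risk difference after rounding was 0.287 against 0.293 with complete data, a shift of 0.6 points. That is somewhat larger than 0.2, partly because one residual variance serves both arms: SD √((0.16+0.25)/2) = 0.453, Φ(0.30/0.453) = 0.746, shift (0.800 − 0.746) × 5/60 = 0.4 points. All of these are small beside a 10-point margin and a 30-point assumed effect.

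**4. Percentage reduction.** The plan gives no distribution. Assume 80% and 50% fully cleared (value 100), the rest uniform on 0–80, and normal draws by arm.

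- Device: mean 0.8·100 + 0.2·40 = 88; variance 0.8·10,000 + 0.2·(80²/3) − 88² = 682.7; SD 26.1; P(>100) = 1 − Φ(12/26.1) = 32.3%.
- Control: mean 70; variance 0.5·10,000 + 0.5·(80²/3) − 70² = 1,166.7; SD 34.2; P(>100) = 1 − Φ(30/34.2) = 19.0%.
- Average: 25.7%, about 26%.

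With the rest uniform on 0–90, the simulation gave about 28% above 100 and about 1% below 0.

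**5. Pooling.** MIANALYZE combines an estimate and its standard error. A Wilcoxon test yields neither unless one is defined, and section 7.5 defines none.

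**The case against.** The strongest reply is that this is an unstated option and not a broken method. PROC MI offers rounding and range limits under MCMC. Imputation applies only if data are missing. The best-case, worst-case and tipping-point analyses use valid 0/1 and 0–100 values and bound the result whatever the imputation method. The secondary test is reached only after superiority succeeds (section 7.8.3). All of this is true, and it is why the expected numeric effect is small. But the plan invokes none of those options, rounding carries the bias shown above, and sensitivity analyses do not make the primary analysis executable.

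A reader might also infer several stronger things that the documents do not support.

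- **That site is imputed.** It is listed as a predictor, and randomization is done separately within each site (section 5.2), so it is known for every randomized subject. The issue is only how it is coded.
- **That the rank test cannot be computed.** It can be, on values above 100. The fault is false ordering at the ceiling and the missing definition of what is pooled.
- **That the method costs the secondary test real power.** A comparison with full data mixes in ordinary information loss, and in reruns normal imputation did no worse than dropping the missing subjects. No loss beyond that was shown.
- **That a rounding rule would be chosen with outcomes in view.** The plan is silent on timing.
- **That the imputation method explains the larger shift seen with the listed predictors.** In the simulation the risk difference fell from 0.295 to 0.271 with those predictors, which do not include treatment arm. Most of that reflects the missing arm term, which is a separate matter.

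**Conclusion.** Wrong as written, with a small expected numeric effect. The method named in section 7.5 produces outcomes that the section 7.4 logistic regression cannot accept, so the primary ITT analysis needs a step that the plan does not state. About one third of imputed binary values fall outside 0–1 and none is 0 or 1. Rounding would shift the device arm by about 0.2 points at the planned loss, and the simulated risk difference by 0.6 points. For the secondary endpoint, about 26% of imputed percentages would exceed 100.

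This rests on four assumptions: default MCMC settings, since no others are given; 5 of 60 missing per arm, completely at random; the assumed 80% and 50% rates; and, for the percentage, a spike at 100 with the rest uniform, which the plan does not state. It also takes section 7.2's ITT population as primary. The Protocol Summary names a per-protocol primary analysis, and section 7.2 imputes nothing in that population.

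The gain from correction is a primary analysis that is valid and can be run as pre-specified, not a material change in the expected result.

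**What to change.** In section 7.5, items 1 and 2:

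1. Replace MCMC with PROC MI FCS. Use LOGISTIC for the binary primary endpoint, and REGPMM (predictive mean matching) for percentage reduction so that imputed values stay within the observed range.
2. Declare site as CLASS. Dysplasia has two levels and may stay as a 0/1 variable.
3. For each test, name the estimate and standard error that MIANALYZE pools. For the primary endpoint this is the adjusted difference in proportions that section 7.4 uses for non-inferiority and superiority. For the secondary endpoint, define a rank-based estimate with its standard error, since changing the imputation method alone leaves this open.

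The cost is SAP wording and a few lines of SAS. No extra data, visits or subjects are needed, and the stated power is unaffected. The change should be made before the data are unmasked.

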7.2 Analysis Populations

The safety analysis population is defined as all subjects who are treated with either EndoRotor® or continued ablative therapy. Subjects will be analyzed as treated.

The primary effectiveness analysis population is intent to treat (ITT), defined as all subjects who are randomized. Subjects will be analyzed as randomized. Missing primary and secondary endpoint data will be imputed.

A supportive effectiveness analysis population is Per Protocol (PP). This population is a subset of ITT and requires that subjects be treated with either EndoRotor® or continued ablative therapy, meet all inclusion/exclusion criteria, and are evaluated for effectiveness at no fewer than two post-treatment visits 3 months apart. Subjects will be analyzed as treated. Missing data will not be imputed.

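### Section 7.5 omits treatment arm from the imputation model for both effectiveness endpoints, so the imputed ITT difference shrinks by about the missing fraction

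*Combined protocol and SAP*

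**What the plan says.** Section 7.2 makes ITT, all randomized subjects, the primary effectiveness population and states: "Missing primary and secondary endpoint data will be imputed". Section 7.4 tests treatment arm in a logistic regression adjusted for age, dysplasia grade, lesion length and disease duration, and refers to Section 7.5 for the imputation.

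Section 7.5, item 1, says that "ten imputations of missing binary primary endpoint will be produced using SAS PROC MI using the Markov chain Monte Carlo algorithm". It then fixes the model: "The following variables will be used as predictors: site, subject's age, dysplasia (low-grade or high-grade), length of Barrett's lesion in cm", and disease duration in months. Item 2 gives the same five variables for percentage reduction, the secondary endpoint. Neither item lists arm, neither says that imputation is run separately by arm, and no other section adds it.

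The sensitivity rules in the same section do distinguish the arms, for example: "The best-case scenario will assume success for all missing data treated with EndoRotor and failure for all missing data treated with control". The omission is therefore specific to the imputation model.

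On size, Section 4.5 plans 120 subjects "to reach a total of 110 evaluable subjects, allowing for 10 subjects lost to follow-up", and Section 7.3 says the study "will have 91.6% power to demonstrate superiority of EndoRotor® over continued ablative therapy".

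**The concern.** An imputation model should contain every variable in the analysis model, above all the one whose effect is estimated. Here the analysis model has arm and the imputation model does not. Randomization balances the five listed variables between arms, so they cannot stand in for arm. Missing outcomes in both arms are then drawn from one pooled distribution, and the completed data mix a real difference among observed subjects with no difference among imputed ones.

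At stake are the primary estimate, superiority power and, because Section 7.8.3 tests the secondary endpoint only after superiority is shown, the chance of reaching that test.

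A second, smaller point: PROC MI's MCMC method draws from a multivariate normal model. Imputed values of a binary endpoint are then not 0 or 1 and cannot enter the logistic regression of Section 7.4 as a binary response. No rounding rule is given.

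**Working it through.** **Inputs from the documents.** Rates 80% and 50%, 55 evaluable per arm (7.3); 120 enrolled, 10 lost (4.5), so f = 10/120 = 8.3%; 1:1 allocation (5.2); two-sided 0.05 (7.1); non-inferiority margin 10 points (7.6); ten imputations (7.5).

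**Assumptions.** Missing completely at random and equally by arm; covariate and site effects set to zero; 4 sites; 20% missing as a second scenario.

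**The plan's own power.** With the pooled-variance normal formula and n = 55 per arm:

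- null SE = √(2 × 0.65 × 0.35 / 55) = 0.0910
- alternative SE = √((0.16 + 0.25) / 55) = 0.0863
- power = Φ((0.30 − 1.96 × 0.0910) / 0.0863) = 92.1%

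Other methods give 89.1% (Fisher), 92.1% (arcsine), 92.6% (exact chi-square) and 93.5% (unpooled). The stated 91.6% is reproduced to within method choice.

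**Shrinkage by algebra.** Without arm, imputed outcomes follow the pooled rate, (0.80 + 0.50)/2 = 0.65. Each arm's expected rate is (1 − f) × own rate + f × 0.65, so the expected difference is (1 − f) × 30 points.

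- f = 8.3%: 78.75% − 51.25% = 27.5 points
- f = 20%: 77% − 53% = 24.0 points
- all 10 losses in one arm: 27.3 points, a shrinkage of 9.1%

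Putting the shrunken rates into the same power formula at 60 per arm gives about 89.5% at 8.3% missing, against 92.1% from the 55 observed per arm. At 20% missing it gives 79.5% against 88.1%.

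**Simulation.** 60 per arm, ten imputations, Rubin's rules, 8000 trials per setting. The logistic rows use the planned covariate-adjusted logistic regression and the lower 95% limit of the predicted proportion difference.

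| Missing | Imputation; analysis | Difference in points, without / with arm | Superiority power, without / with arm |
|---|---|---|---|
| 8.3% | logistic draws; adjusted logistic | 27.2 / 29.7 | 88.8% / 91.6% |
| 8.3% | unrounded normal draws; unadjusted | 27.3 / 29.9 | 88.4% / 91.6% |
| 20% | logistic draws; adjusted logistic | 23.8 / 29.6 | 75.7% / 87.0% |
| 20% | unrounded normal draws; unadjusted | 24.0 / 30.0 | 73.4% / 86.5% |

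The Monte Carlo standard error at 91.6% is √(0.916 × 0.084 / 8000) = 0.3 point. Separate runs of 3000 trials, with a linear imputation model and Bernoulli, rounded or unrounded draws, agree. Without arm, the ratio of estimated to true difference is 0.915 to 0.919 at 8.3% missing and 0.785 to 0.799 at 20%, against 1 − f = 0.917 and 0.80.

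**Non-inferiority error.** At a true difference of −10 points (40% against 50%, logistic draws), false non-inferiority without / with arm is 2.5% / 2.9% at 8.3% missing and 1.9% / 3.1% at 20%. The estimate moves toward zero (−10 becomes about −9.2 at 8.3%), but Rubin's variance is overstated, so the error does not rise.

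**Secondary endpoint.** For assumed means of 85 and 65 with SD 25 (4000 trials), the mean difference without arm is 18.4 points at 8.3% missing and 16.0 at 20%, against 20.1 and 20.0 with arm.

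**Normal draws of a binary endpoint.** At a pooled 65%, the SD is √(0.65 × 0.35) = 0.477. The share of draws outside 0 to 1 is Φ(−0.65/0.477) + Φ(−0.35/0.477), about 32%. With arm included, unrounded draws give 29.9 points and draws rounded at 0.5 (an assumed rule) give 29.3 at 8.3% missing. This gap is not what causes the shrinkage.

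**The case against.** The best reply is that the effect is modest and safe. At the planned loss it is about 2.5 points on the difference and 2 to 3 points of superiority power. The gap from 91.6% to 88.8% lies inside the 89.1% to 93.5% spread between test methods, and Section 4.7 states 90% for the same design. The bias is conservative for superiority and does not inflate false non-inferiority. The best-case, worst-case and tipping-point analyses, and a Per Protocol analysis without imputation, stand beside it. The 20% scenario is not in the documents.

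Much of this is right. The size at 8.3% is modest, and the fair measure of lost power is with arm against without arm under one method; that comparison shows a loss every time. The remaining arguments do not remove the problem. The sensitivity analyses bound extremes and the Per Protocol set is only supportive, so neither corrects the primary estimate. Missingness could also exceed 8.3%. ITT counts everyone randomized, randomization can precede the procedure by up to two weeks (5.2), and subjects found ineligible at the procedure are neither treated nor followed (5.5.2). The documents give no figure for this.

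For the secondary endpoint, only the mean difference was evaluated, on assumed values. The effect on the planned Wilcoxon test was not computed.

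**Conclusion.** The concern holds. Followed as written, Section 7.5 biases the primary estimate toward no difference by about the missing fraction times the true difference. At the plan's own 8.3% loss this takes roughly 30 points to 27.2, and superiority power from 91.6% to 88.8% under the same method, so the power stated in 7.3 is not reached. At an assumed 20% missing the estimate is 23.8 points and power 75.7%, against 87.0% with arm. The secondary mean difference shrinks by the same fraction.

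These sizes rest on data missing completely at random, equal missingness by arm, and listed covariates that do not act as proxies for arm. With unequal missingness the shrinkage is close to, but not exactly, the overall missing fraction. No inflation of false non-inferiority was found. The normal-model MCMC point is a separate implementation gap. This should be fixed before unmasking.

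**What to change.** In Section 7.5, add treatment arm to the imputation model for both endpoints, or impute separately by arm, and keep site and the four covariates. For the binary primary endpoint, replace MCMC with fully conditional specification using logistic regression, so that imputed values are 0 or 1. A stated rounding rule would also give 0/1 values, but rounding leaves slightly more shrinkage (29.3 points at 8.3% missing, with arm included).

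Make the change before unmasking; adding arm afterwards would depart from a prespecified list. The cost is SAP wording and a few lines of code, with no effect on sample size, visits or data collection.

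Optionally, add site to the logistic model in Section 7.4, because randomization is within site. With 3 to 5 sites this uses 2 to 4 degrees of freedom. Having site only in the imputation model is not an error.
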